2.4 Potential Risks and Benefits

Patients with severe atopic eczema suffer significant sleep loss because of intractable generalised itching, commonly show poor school attendance and are often socially withdrawn. Attention-deficit hyperactivity disorder has recently been linked to severe atopic eczema, and these patients often go on to develop anxiety and depression(16, 17). Skin infections, in particular with *Staphylococcus aureus* but also herpes simplex, leading to hospital admissions are another typical feature (4, 5). The National Institute for Clinical Excellence guidelines for the treatment of children with severe eczema recommends systemic immuno-suppressive therapy with CyA or MTX(18). Indeed, both CyA and MTX have been used in severe inflammatory skin diseases for many years, including children with uncontrolled psoriasis and atopic eczema and are part of established NHS care and clinical

practice internationally (6). There are also American Academy of Dermatology treatment guidelines for systemic immuno-suppressive therapies in children with severe atopic eczema, which we adhere to in terms of treatment dose and safety monitoring. However, both treatments are used off label in this paediatric patient population, and patient safety is a key secondary outcome measure of the trial.

2.4.1 Potential Risks:

The use of CyA and MTX in children is seen in clinical practice for a large number of diseases and conditions. While malignant diseases, such as lymphoblastic leukaemia and lymphoblastic lymphoma are often treated using high doses, chronic inflammatory conditions, such as juvenile idiopathic arthritis, juvenile dermatomyositis, systemic lupus erythematosus, and scleroderma are treated using lower doses. For severe uncontrolled inflammatory skin diseases, such as psoriasis, typically a therapeutic dose of 0.4mg/kg/week MTX (max 25mg per week) is used(19), as indicated in the Children's British National Formulary, the dose we are using in the TREAT trial. The Children's British National Formulary indicates a therapeutic dose of 5mg/kg/day for CyA severe atopic eczema, while our trial protocol stipulates 4mg/kg/day, although treating TREAT trial physicians can go up to 5mg/kg/day, depending on treatment response.

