As for MTX, gastrointestinal disturbance, in particular nausea, liver function abnormalities and bone-marrow suppression are the main potential side effects, but the medication is well tolerated in the majority of cases and considered safe in the long-term, partly based on the extensive rheumatology and gastroenterology experience in children, using similar if not higher doses for longer periods of time and often in combination with biologics (4, 5, 20-23). In addition, the only RCT using MTX in children with severe atopic eczema over a 12 week period, the following adverse events were recorded: nausea/vomiting (4/20), abdominal pain (1/20), glossitis/oral ulceration (4/20), diarrhoea (5/20), pancytopenia (1/20), anaemia (6/20), leukopenia (2/20), abnormal liver function (5/20), abnormal renal function (1/20), fatique (6/20), headache (3/20), and flu-like symptoms (1/20). This overall favourable side effect profile has been confirmed by three observational studies, involving a total of 102 paediatric patients with treatment durations of up to 38 months (24-26). We are performing safety bloods after the initial test dose for MTX to capture rare idiosyncratic reactions early and review participants in both study arms with safety bloods and enquiry about adverse events fortnightly for the first month, then monthly until week 12 and then eight-weekly, while on treatment, in keeping with the American Academy of Dermatology guidelines for the use of these systemic agents in children with severe atopic eczema(27). Patients are also encouraged to contact the study team in case of any concerns about drug adverse reactions

between study visits. In addition, all potential participants and their parents will be informed about common and rare serious side effects in the Patient Information Leaflets and also instructed to contact the study team/seek medical advice straight away if any of the following occur:

Methotrexate:

- Infections, including fever (temperature above 38°C), chills, sore throat or chicken pox
- Skin rash, changes in nail or skin colour, or skin ulcers
- Jaundice
- Bleeding gums, unexpected bruising or bleeding that doesn't stop as quickly as normal
- Melaena
- Chest pain, difficulty breathing or chronic dry cough
- Severe and continuing diarrhoea, vomiting or stomach pains

Ciclosporin:

- Infections, including fever (temperature above 38°C), chills, sore throat or chicken pox
- Unusual bleeding that is difficult to stop
- Severe bruising

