7.2.3 Ciclosporin - Dose Modifications

Patients should remain on the full treatment dose (4mg/kg/day for CyA) for the 12 weeks. After that, dose increases to a maximum of 5mg/kg/day or dose decreases are allowed, according to the treatment response. For decisions on treatment continuation, Pls should refer to the table below. For situations not included in the below table, this is down to the individual study centre Pl and any dose changes will be recorded in the CRF.

Table 5: Dose modification schedule

Note: any events that meet the monitoring parameters in the table below should be recorded and reported as an adverse event (see section 10.7)

Monitoring parameters	Values	Action
eGFR	Fall of >=20% (compared with eGFR value that was used to confirm eligibility)	Repeat renal profile should be done within 2 weeks of the last visit. If eGFR falls again >=20 % following repeat bloods, the trial nephrologist must be contacted to discuss potential dose reduction. If repeat bloods cannot be obtained within 2 weeks of the last visit, the trial nephrologist must be contacted within 48 hours of the site becoming aware that a repeat renal profile cannot be obtained within the timeframe (2 weeks), to discuss potential dose reduction.
Blood pressure	>95 th centile for age and sex on two consecutive visits	CyA dose adjustment, reduction by at least 20% initially and patient review. A temporary dose suspension at the PI's discretion is permitted. Repeat BP after a fortnight.
Liver function test	AST, ALT or alkaline phosphatase more than 2× upper limit of reference range	CyA dose adjustment reduction by at least 20% initially or a temporary dose suspension at the Pl's discretion. Repeat LFT weekly until normal. Further reductions in dose or stopping medication may be required but should be discussed with the Chief Investigator.
Platelet count	<100x10 ⁹ /L	CyA dose adjustment reduction by at least 20% initially or a temporary dose suspension at the PI's discretion. Repeat platelets weekly until normal. Further reductions in dose or stopping medication may be required but should be discussed with the Chief Investigator.
Neutrophil count	<1.5x10 ⁹ /L	CyA dose adjustment reduction by at least 20% initially or a temporary dose suspension at the PI's discretion. Repeat neutrophils weekly until normal. Further reductions in dose or stopping medication

		may be required but should be discussed with the Chief Investigator.

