7.3.2 Methotrexate - Preparation, Dosage and Administration of Study Treatment/s

Table 7: Methotrexate tablets/ subcutaneous injection/oral solution

	Methotrexate tab	lets / subcutane	eous injection/ o	oral solution	
Dose	Initial dose of 0.1mg/kg/week, then 0.4mg/kg/week from week 1 (maxid 25mg/week)			from week 1 (maximum	
	For patients ≥ 22kg, doses should be rounded as per table below irrespective of formulation.				
	Weight band 0.1mg/kg test dose 0.4mg/kg dose				
	<22kg	no rounding r	equired		
	22 to <29 kg	2.5mg	10mg		
	29 to <36 kg	2.5mg	12.5mg		
	36 to <43 kg	5mg	15mg		
	43 to <50 kg	5mg	17.5mg		
	50 to <57 kg	5mg	20mg		
	57 to <63kg	5mg	22.5mg		
	63kg +	7.5mg	25mg		
Eroguanav	syringe.			2.5mg and 5mg pre-filled	
Frequency	Weekly				
Duration	36 weeks				
Route	Oral or subcutaneous				
Formulation	Decision about formulation used to be made by local clinician, taking into				
Note	account patient's preference The methotrexate dosing regimen reflects current clinical practice across				
	European paediatric dermatology departments (based on TREAT survey among >300 paediatric dermatologists from 8 European countries) (6). It is also in keeping with the British National Formulary guidance for the treatment of severe cutaneous inflammatory disease in children (19), and that of the American Academy of Dermatology for severe paediatric eczema (27).				
It is acknowledged that extra precaution is necessary when predispensing methotrexate and the following additional measure should be implemented for this trial in line with standard clinical. The child and their parents/carers must be carefully advised frequency and the reason for taking methotrexate and folic action. Only the 2.5mg strength of methotrexate tablet will be present dispensed. The prescription and the dispensing label will clearly show the frequency of methotrexate administration. The child and their parents/carers will be provided with a mean monitoring booklet which will provide additional supporting information and adverse effects monitoring.		al measures as listed below dard clinical care: ly advised of the dose and and folic acid at each visit. Il be prescribed and and show the dose and with a methotrexate drug			

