7.3.3 Methotrexate - Dose Modifications

Patients will start on an initial test dose (0.1/mg/kg/week) for MTX (week 0) and then continue on the full treatment dose (0.4mg/kg/week for MTX – maximum dose of

34

IRAS: 182752

25mg/week) from the following week (week 1), providing there have not been any significant side effects and the results from the safety bloods are acceptable (see Table 7).

Please note if the results from the patient's week 1 safety bloods indicate a degree of toxicity to the initial test dose for MTX but the results are within the trial monitoring parameters (see Table 7), a review by the principal investigator and the chief investigator is required, before a dose adjustment is made.

Patients should remain on the full treatment dose (0.4mg/kg/week for MTX – maximum dose of 25mg/week) until week 12 (visit 5). After that, dose modifications are allowed, according to the treatment response (maximum dose of 25mg/week). For decisions on treatment continuation, PIs should refer to the table below. For situations not included in the below table, this is down to the individual study centre PI and any dose changes will be recorded in the CRF.

Table 8: Methotrexate dose modification schedule

Note: any events that meet the monitoring parameters in the table below should be recorded and reported as an adverse event (see section 10.7)

Monitoring parameters	Values	Action
eGFR	Fall of >=20% (compared with	Repeat renal profile should be
	eGFR value that was used to	done within 2 weeks of the last
	confirm eligibility)	visit. If eGFR falls again >=20
		% following repeat bloods, the
		trial nephrologist must be
		contacted to discuss potential
		dose reduction. If repeat bloods
		cannot be obtained within 2
		weeks of the last visit, the trial
		nephrologist must be contacted within 48 hours of the site
		becoming aware that a repeat
		renal profile cannot be obtained
		within the timeframe (2 weeks),
		to discuss potential dose
		reduction.
Blood pressure	>95 th centile for age and sex on	MTX dose adjustment,
	two consecutive visits	reduction by at least 20%
		initially and patient review. A
		temporary dose suspension at
		the PI's discretion is permitted.
		Repeat BP after a fortnight.
Liver function test	AST, ALT or alkaline phosphatase	MTX dose adjustment
	more than 2x upper limit of	reduction by at least 20%
	reference range	initially or a temporary dose
		suspension at the PI's
		discretion.
		Repeat LFT weekly until

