		normal. Further reductions in
		dose or stopping medication may be required but should be
		discussed with the Chief
		Investigator.
		mvostigator.

Platelet count	<100x10 ⁹ /L	MTX dose adjustment reduction by at least 20% initially or a temporary dose suspension at the PI's discretion. Repeat platelets weekly until normal. Further reductions in dose or stopping medication may be required but should be discussed with the Chief Investigator.
Neutrophil count	<1.5x10 ⁹ /L	MTX dose adjustment reduction by at least 20% initially or a temporary dose suspension at the PI's discretion. Repeat neutrophils weekly until normal. Further reductions in dose or stopping medication may be required but should be discussed with the Chief Investigator.
Unexplained bruising, chicken pox contact or rash suspected to be chicken pox infection	Not applicable	Review by the PI prior to continuing with MTX.
New or worsening unexplained dyspnoea or cough	Not applicable	Review by the PI prior to continuing with MTX

The MTX dose/route should remain within the trial parameters (0.4mg/kg/week, maximum dose of 25mg/week/patient) until week 12 (visit 5) on the therapeutic dose. During the first 12 weeks, a dose increase is acceptable for growth (at same dose/kg as at trial entry).

Methotrexate treatment may be suspended for clinical reasons. If for any reason a patient misses a treatment dose, this will be documented in the patient diary but the patient should not discontinue trial treatment or be withdrawn from the trial. Patients who discontinue trial treatment should be asked to continue with study assessments.

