8.3 Procedures for Assessing Safety

The following safety bloods and investigations will be performed:

- a. Safety blood profiles (full blood count, renal function and liver function) will be taken at screening, 2, 4, 8, 12, 20, 28, 36 and 60 weeks. Lipids will also be assessed at screening and week 4 as part of the safety blood profile. Safety bloods will also be taken at week 1 for the methotrexate arm. If it is not possible to obtain a safety blood sample (e.g. insufficient sample, participant refusal) at their visit, the remaining trial procedures can be carried out as normal and the patient can continue in the trial. However, the participant should be advised to temporarily stop trial treatment, until further advice is sought. The CTU should be contacted with the following information:
 - · Details of which safety blood values are missing
 - Date started treatment
 - Date and reason of any dose changes previously required
 - Details of any previous blood samples that had safety implications
 - Date of next scheduled visit

CTU will then liaise with CI (or delegate) and sponsor and will advise the site regarding the necessity to arrange an unscheduled visit to obtain missing safety assessment/s and when to reintroduce trial treatment. If a participant is not able to comply with the requested measures then permanent discontinuation of trial treatment may be considered, though in these circumstance the participant will be asked to continue in the study for follow-up purposes.

Please note, the above process does not apply to safety bloods taken at week 1 for the methotrexate arm, as this sample must be taken.

- b. BP will be taken at baseline, 2, 4, 8, 12, 20, 28, 36 and 60 weeks
- c. Chest X-Ray in those at risk of TB (discretion of local PI/medically qualified physician) at screening visit
- d. Physical examination will be carried out at each visit (except at the screening visit).

An Independent Data and Safety Monitoring Committee (IDSMC) will be constituted and will monitor adverse events and patient safety during the trial. Data on adverse events, including severity, seriousness, and expectedness as part of pharmacovigilance will be recorded at each follow-up visit and communicated to the CTRC. Requirements for pharmacovigilance reporting is detailed fully in Section 10 (Pharmacovigilance).

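### After week 12 the only methotrexate limit stated in 7.3.3 is 25 mg/week, with no per-kg ceiling, so for lighter children the maximum dose is either several-fold too loose or undefined

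*Protocol*

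**What the plan says.** **Methotrexate up to week 12.** Section 7.3.3 states: "The MTX dose/route should remain within the trial parameters (0.4mg/kg/week, maximum dose of 25mg/week/patient) until week 12 (visit 5) on the therapeutic dose". It adds: "During the first 12 weeks, a dose increase is acceptable for growth (at same dose/kg as at trial entry". In 7.3.2, Table 7 converts 0.4 mg/kg into weight bands from 22 kg upwards ("doses should be rounded as per table below irrespective of formulation"), with no rounding below 22 kg.

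**Methotrexate after week 12.** Section 7.3.3 states: "After that, dose modifications are allowed, according to the treatment response (maximum dose of 25mg/week". It gives no mg/kg figure and no step size.

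**Ciclosporin after week 12.** Section 7.2.3 states: "After that, dose increases to a maximum of 5mg/kg/day or dose decreases are allowed, according to the treatment response". The starting dose is 4 mg/kg/day.

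**Justification.** Section 2.4.1 presents 0.4 mg/kg/week (max 25 mg) as the children's formulary dose and the dose used in this trial. For ciclosporin it gives 5 mg/kg/day as the formulary dose and notes escalation: "although treating TREAT trial physicians can go up to 5mg/kg/day, depending on treatment response". It describes no escalation for methotrexate.

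**Monitoring.** Section 2.4.1 schedules review with safety bloods fortnightly for the first month, "then monthly until week 12 and then eight-weekly, while on treatment". Section 8.3 says the blood profiles "will be taken at screening, 2, 4, 8, 12, 20, 28, 36 and 60 weeks", plus week 1 in the methotrexate arm.

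**The concern.** Two sentences in 7.3.3 tie the per-kg limit to the first 12 weeks, and the sentence governing the later period carries only an absolute cap. An absolute cap set for a child of 63 kg or more does not restrain dosing in a small child. The trial enrols from age 2, and Table 7 expressly provides for children under 22 kg.

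The first issue is safety. On its literal wording the protocol permits weekly doses well above the one it justifies, in the lightest participants, during the period when scheduled bloods are most widely spaced.

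The second is consistency. If some sites take 25 mg as the limit and others take 0.4 mg/kg, the methotrexate strategy in weeks 12 to 36 is not the same at every site, and the week-36 severity and toxicity results would describe a mixture of the two.

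**Working it through.** **Inputs.** Table 7 weight bands and doses (7.3.2); the 25 mg/week limit (7.3.3); ciclosporin 4 and 5 mg/kg/day (7.2.3); visit schedule and windows (8.1, 8.3).

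**Step 1: reproduce Table 7.** Multiplying 0.4 mg/kg by the edges of each band gives 8.8 to 11.6 mg for 22 to <29 kg (table: 10 mg), 20.0 to 22.8 mg for 50 to <57 kg (table: 20 mg), and 25.2 mg at 63 kg (table: 25 mg). The 25 mg cap starts to bind at 25 / 0.4 = 62.5 kg, which matches the table's top band of 63 kg and over. So 25 mg is the 0.4 mg/kg dose only for the heaviest children.

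**Step 2: permitted rise after week 12, literal reading.** Fold rise = 25 / Table 7 dose. Resulting dose per kg = 25 / weight at each band edge.

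| Weight | Table 7 dose (mg/week) | Fold rise to 25 mg | mg/kg/week at 25 mg |
|---|---|---|---|
| 22 to <29 kg | 10 | 2.50 | 1.14 to 0.86 |
| 29 to <36 kg | 12.5 | 2.00 | 0.86 to 0.69 |
| 36 to <43 kg | 15 | 1.67 | 0.69 to 0.58 |
| 43 to <50 kg | 17.5 | 1.43 | 0.58 to 0.50 |
| 50 to <57 kg | 20 | 1.25 | 0.50 to 0.44 |
| 57 to <63 kg | 22.5 | 1.11 | 0.44 to 0.40 |
| 63 kg and over | 25 | 1.00 | 0.40 or less |

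Below 22 kg the dose is unrounded, so the fold rise is 25 / (0.4 × weight). At the 22 kg boundary this is 25 / 8.8 = 2.84, and it grows as weight falls. The protocol gives no weight distribution, so the following weights are assumptions:

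- 20 kg: 8 to 25 mg, 3.1-fold, 1.25 mg/kg/week
- 15 kg: 6 to 25 mg, 4.2-fold, 1.67 mg/kg/week
- 12 kg: 4.8 to 25 mg, 5.2-fold, 2.08 mg/kg/week

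**Step 3: the same quantity under the restrictive reading.** If 0.4 mg/kg/week remains the ceiling, the permitted rise is 1.0-fold at every weight, apart from growth. For a child of 22 to <29 kg the two readings therefore give maxima of 10 and 25 mg/week.

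**Step 4: ciclosporin for reference.** 5 / 4 = 1.25-fold at every weight. The relevant contrast is the kind of limit, which scales with body size for ciclosporin and does not for methotrexate.

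**Step 5: time to the next scheduled bloods.** Visit 5 to visit 6 is 20 − 12 = 8 weeks. With ±2 weeks on each visit the gap runs from 18 − 14 = 4 to 22 − 10 = 12 weeks. By comparison, the initial step from 0.1 to 0.4 mg/kg at week 1 is conditional on acceptable week-1 bloods and is followed by bloods at weeks 2 and 4.

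**The case against.** The strongest reply is that the per-kg limit was never meant to lapse. The protocol summary, 2.4.1 and Table 7 all give 0.4 mg/kg/week without an end date, and Table 7 states a duration of 36 weeks. Each pairs that dose with the 25 mg cap, so the parenthesis in 7.3.3 may simply repeat the cap. Where increases above the base dose were intended, for ciclosporin, the protocol says so outright; for methotrexate it speaks only of modifications. The hold to week 12 covers dose and route together, so its lapse could mean only that decreases and route changes become possible. Sections 7.1 and 7.3.2 also describe the methotrexate dosing as in line with product information, formulary and dermatology guidance.

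Much of this stands. It rules out treating the lifting of the limit as an established fact. It does not settle the matter the other way: Table 4 likewise gives ciclosporin 4 mg/kg/day for 36 weeks although 7.2.3 allows 5, so a base-dose table does not by itself override a modification section. The same-dose-per-kg condition in 7.3.3 is also expressly confined to the first 12 weeks.

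A second reply is that safeguards exist. Table 8 calls for a reduction of at least 20% or a suspension, with weekly repeats, for abnormal liver tests, platelets or neutrophils. Unscheduled visits can include bloods when these are part of the reason for the visit. Eight-weekly bloods apply to both arms and are stated to follow a guideline. These measures reduce the risk, but they respond to a problem once it is found and set no ceiling.

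A reader might also infer that unequal percentage headroom between the arms is itself a fault, or that the flare co-primary is biased. The documents support neither. Two different drugs need not share a percentage margin, and response-guided dosing in weeks 12 to 36 is openly part of both strategies. Flare is defined by return to baseline o-SCORAD or restarting systemic treatment. The number of children whose dose would be raised is unknown, and the two readings push any imbalance in opposite directions.

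**Conclusion.** The point holds as a badly fixed dosing limit. Read literally, 7.3.3 permits a 2.5-fold rise at 22 to <29 kg and more than 2.8-fold below 22 kg, above the 0.4 mg/kg/week that 2.4.1 supports. Read restrictively, it permits no rise at all. The wording does not decide between them, and 25 mg/week alone does not protect a small child.

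The banded figures rest only on Table 7 and the 25 mg limit; those for particular weights below 22 kg rest on assumed weights. All are permitted maxima: they do not predict what clinicians would prescribe. Dosing is held until week 12, so the week-12 co-primary is unaffected, and no effect on the flare co-primary can be derived. The point merits a correction chiefly for paediatric safety and for uniform practice across sites.

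**What to change.** In 7.3.3, replace the bare 25 mg/week limit that applies after week 12 with a per-kg ceiling. Default wording: *not above 0.4 mg/kg/week rounded per Table 7, maximum 25 mg/week*. The reference to Table 7 is needed because rounding already puts some children slightly above 0.4 mg/kg (10 mg at 22 kg is 10 / 22 = 0.455 mg/kg).

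If the sponsor does intend increases for poor response, name the higher mg/kg ceiling instead and require safety bloods about 2 weeks after each increase. The level of that ceiling is a clinical decision for the sponsor.

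**Cost.** One wording amendment. Both options reduce investigator freedom in weeks 12 to 36. The default needs no extra visits but leaves methotrexate without upward titration while ciclosporin has it, which should be stated as a deliberate choice. The alternative adds about one blood test per dose increase. Neither alters the week-12 endpoint or the end of treatment at week 36.
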